8.4.3 Electrocardiogram (ECG)

A standard 12 lead ECG will be performed as described in [Table 8-6](#).

ECG assessment needs are similar for all patients up to week 48.

Patients dose escalating to 200 mg q.d. (as outlined in [Section 6.6.2](#)) must have ECG assessments performed:

- on the day of dose escalation (pre-dose and between 2h to 3h post-dose ECGs are required),
- two weeks post-dose escalation,
- at next 2 quarterly visits (at 3 and 6 months post-dose escalation),
- every 6 months thereafter.

Please refer to ([Table 8-6](#)) below for more details.

After the subject has rested approximately 5 minutes in a supine position, standard 12- lead ECGs must be obtained in triplicate with a recommended interval of 5 minutes between each ECG reading.

The preferred sequence of cardiovascular data collection during study visits is ECG collection first, followed by vital signs and then blood sampling. The Fridericia QT correction formula (QTcF) should be used for clinical decisions. The investigator must calculate QTcF if it is not auto-calculated by the ECG machine.

ECGs will be locally collected and evaluated. Interpretation of the tracing must be made by a qualified physician and documented on the ECG CRF page. Each ECG tracing should be labeled with the study number, patient initials (where regulations permit), subject number, date, and kept in the source documents at the study site.

Table 8-6 Local ECG collection plan

Week	Day	Time
Screening/Baseline	Day -28 to -1	3 serial, 12 lead ECGs
1		3 serial, 12 lead ECGs between 2h to 3h post-dose
2		3 serial, 12 lead ECGs between 2h to 3h post-dose
4		3 serial, 12 lead ECGs
12		3 serial, 12 lead ECGs
24, 48		3 serial, 12 lead ECGs
For patients not dose escalating: Week 60, 84, 108, 132		3 serial, 12 lead ECGs
For patients dose escalating: Dose escalation visit (Week 60 or Week 72, 84, 96, 108, 120)		3 serial, 12 lead ECGs pre-dose and between 2h to 3h post-dose
Two weeks post dose escalation visit (Week 62 or Week 74, 86, 98 110, 122)		3 serial, 12 lead ECGs
Twelve weeks post dose escalation visit (Week 72 or Week 84, 96, 108, 120, and 132).		3 serial, 12 lead ECGs
Twenty-four weeks post dose escalation visit (Week 84 or Week 96, 108, 120, 132 and EOT)		3 serial, 12 lead ECGs
EOT		3 serial, 12 lead ECGs
Unscheduled or Unplanned ECG		3 serial, 12 lead ECGs

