2.1.1 General definitions

Investigational drug and study treatment

Investigational drug, will refer to asciminib. No additional treatment beyond investigational drug is included in this trial.

Treatment groups

- Asciminib 40 mg b.i.d. (Subjects randomized to asciminib 40 mg b.i.d. at the beginning of the study)
- Asciminib 80 mg q.d. (Subjects randomized to asciminib 80 mg q.d. at the beginning of the study)

The standard dose for all subjects in this study is asciminib 40 mg b.i.d. or 80 mg q.d. For subjects not achieving MMR at 48 weeks or losing the response after the week 48 assessment up to week 108, a dose escalation to 200 mg q.d. may be considered per investigator decision.

Date of end of study treatment (EOsT)

The EOsT date is the date that the study treatment is ended for the entire study. On this date, subjects are treated for at maximum 144 weeks, unless subjects have discontinued study treatment earlier.

Date of first administration of study treatment

The date of first administration of study treatment is derived as the first date when a non-zero dose of study treatment was administered as per the Study Treatment electronic case report form (eCRF). The date of first administration of study treatment will also be referred as start of study treatment.

The date of first administration of study treatment is the same as the date of first administration of investigational drug.

Start Date of dose escalation

The start date of dose escalation is derived as the first date when a subject had dose escalated to 200 mg q.d. of study treatment as per the Subject Status Dose Escalation case report form (eCRF).

Date of last administration of study treatment

The date of last administration of study treatment is defined as the last date when a non-zero dose of study treatment was administered as per Study Treatment eCRF.

The date of last administration of study treatment is the same as the date of last administration of investigational drug.

Study day

The study day, describes the day of the event or assessment date, relative to the reference start date.

The study day is defined as:

- The date of the event (visit date, onset date of an event, assessment date, etc.) – reference start date + 1 if event is on or after the reference start date;
- The date of the event (visit date, onset date of an event, assessment date, etc.) – reference start date if event precedes the reference start date.

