The reference start date for safety assessments (e.g. adverse event onset, laboratory abnormality occurrence, vital sign measurement, dose interruption, etc.) is the start of study treatment.

The reference start date for all other, non-safety assessments (e.g. molecular response, disease progression, ECOG performance status, patient reported outcomes (PRO), etc.) is the date of randomization.

The reference start date for dose escalation (200 mg q.d.) is the date when a subject starts first escalated dose.

The study day will be displayed in the data listings. If an event starts before the reference start date, the study day displayed on the listing will be negative.

Time unit

A year length is defined as 365.25 days. A month length is 30.4375 (=365.25/12) days. If duration is reported in months, duration in days will be divided by 30.4375. If duration is reported in years, duration in days will be divided by 365.25.

A week length is defined as 7 days. If duration is reported in weeks, duration in days will be divided by 7.

Baseline for the treatment period

For efficacy evaluations, the last non-missing assessment, including unscheduled assessments on or before the date of randomization is taken as “baseline” value or “baseline” assessment. In the context of baseline definition, the efficacy evaluations also include PRO and performance status.

For safety evaluations, the last available assessment, including unscheduled assessments before the date of start of study treatment is taken as “baseline” assessment.

For pre-dose electrocardiogram (ECG), the last available assessment before the treatment start date is used for baseline.

For ECGs requiring triplicate measures per time point, the average of these measurements will be reported by sites in eCRF baseline.

For mutations, the screening/baseline assessment is taken as “baseline” assessment.

In rare cases where multiple laboratory measurements meet the baseline definition, with no further flag or label that can identify the chronological order, then the following rule should be applied: If values are from central and local laboratories, the value from central assessment should be considered as baseline.

If subjects have no value as defined above, the baseline result will be missing.

On-treatment assessment/event and observation periods

For adverse event reporting the overall observation period will be divided into three mutually exclusive segments:

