1. ***pre-treatment period:*** from day of subject’s informed consent to the day before first administration of study treatment
2. ***on-treatment period:*** from date of first administration of study treatment to 30 days after date of last administration of study treatment (including start and stop date).
3. ***post-treatment period:*** starting at day 31 after last administration of study treatment.

If dates are incomplete in a way that clear assignment to pre-, on-, post-treatment period cannot be made, then the respective data will be assigned to the on-treatment period.

Safety summaries (tables, figures) on the corresponding Safety set include only data from the on-treatment period with the exception of baseline data which will also be summarized where appropriate (e.g. change from baseline summaries). In particular, summary tables for adverse events (AEs) will summarize only on-treatment events, with a start date during the on-treatment period. In addition, a separate summary for death will be provided.

However, all safety data (including those from the pre-treatment and post-treatment) will be listed and flagged as appropriate.

Efficacy summaries on the FAS and FAS 2 (apart from OS and PFS) include data from baseline up to either the last assessment on or before the End of Treatment (EoT) visit or before or on treatment failure, whichever is the earliest.

The efficacy assessments collected post-treatment failure or post-EoT visit are not included in any efficacy analyses (except for OS and PFS analyses). However, they will be listed and flagged as appropriate.

Windows for multiple assessments

Data such as molecular response, cytogenetic response collected over time (including unscheduled visits) will be summarized by scheduled time point. As subjects do not always adhere to the visit schedule, visits will be remapped according to visit windows defined in Tables 2-1 to Table 2-3 of this document to enable by-visit analysis. Only those protocol-defined visits will have the visit window defined. Each assessment (including the end of treatment assessment), either scheduled or unscheduled, will have a mapped visit assigned, as long as study day is available, according to the defined visit window up to the date with data included.

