2.7.3 Laboratory data

Clinical laboratory evaluations

All laboratory data will be summarized by visit/time. Shift tables using the low/normal/high/ (low and high) classification will be used to compare baseline to the worst on-treatment value.

Grading of laboratory values will be assigned programmatically as per NCI Common Terminology Criteria for Adverse Events (CTCAE) version 5. The calculation of CTCAE grades will be based on the observed laboratory values only, clinical assessments will not be taken into account.

CTCAE Grade 0 will be assigned for all non-missing values not graded as 1 or higher. Grade 5 will not be used. Details of CTCAE grading and imputation rules are presented in [Appendix 5.3](#).

For laboratory tests where grades are not defined by CTCAE version 5.0, results will be categorized as low/normal/high based on laboratory normal ranges.

On analyzing laboratory data, all sources (central and local laboratories) will be combined. The summaries will include all assessments available for the lab parameter collected no later than 30 days after the last study treatment administration date.

The following summaries will be generated on the corresponding Safety set (SAF, SAF 2) separately for hematology, and biochemistry laboratory data (by laboratory parameter):

- Worst post-baseline CTCAE grade (regardless of the baseline status). Each subject will be counted only for the worst grade observed post-baseline in the on-treatment period.
- Shift tables using CTCAE grades to compare baseline to the worst on-treatment value.
- For laboratory tests where CTCAE grades are not defined, shift tables using the low/normal/high/(low and high) classification to compare baseline to the worst on-treatment value.

The following listings will be produced separately for hematology and biochemistry for the laboratory data:

- Listings of all laboratory data, with CTCAE grades and classification relative to the laboratory normal range. Lab data collected during the post-treatment period will be flagged.
- Listing of all CTCAE grade 3 or 4 laboratory toxicities

Liver function parameters

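### SAP 2.1.1 separates safety baseline from on-treatment data by calendar date alone, so any Week 1 Day 1 laboratory or vital-sign value taken before the first tablet that day is counted as on-treatment

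*SAP*

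**What the plan says.** All the governing rules are in SAP 2.1.1.

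- **Treatment start** is a date with no clock time: "derived as the first date when a non-zero dose of study treatment was administered".
- **Safety baseline:** "For safety evaluations, the last available assessment, including unscheduled assessments before the date of start of study treatment is taken as" baseline.
- **ECG baseline** uses the same cut: "For pre-dose electrocardiogram (ECG), the last available assessment before the treatment start date is used for baseline".
- **Efficacy baseline** is looser. It allows values "on or before the date of randomization", so a same-day value qualifies there.
- **Pre-treatment period** runs from consent "to the day before first administration of study treatment".
- **On-treatment period** runs "from date of first administration of study treatment to 30 days after date of last administration of study treatment", with both end dates included. Safety summaries use this period plus baseline. Protocol 12.5.2 defines the periods in the same way.

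These rules feed the laboratory tables in SAP 2.7.3, where "Each subject will be counted only for the worst grade observed post-baseline in the on-treatment period", and also the shift tables, the liver-parameter categories and the notable vital-sign counts in SAP 2.7.4.3.

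Protocol Table 8-1 schedules hematology, chemistry, vital signs and weight at Week 1 Day 1 without a time relative to dose. The Week 1 ECG is set at 2 to 3 hours post-dose (Table 8-6). Protocol 8.4.3 adds: "The preferred sequence of cardiovascular data collection during study visits is ECG collection first, followed by vital signs and then blood sampling".

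**The concern.** A value measured before any asciminib has been taken is by nature a baseline value. Under the SAP it is treated as a result on drug whenever it carries the first-dose date, and an older value takes its place as baseline.

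Two effects follow for such values:

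- A worst-value derivation gains one extra, drug-free observation. That can leave the worst grade or liver category unchanged or make it worse; it cannot improve it. The same holds for notable vital signs judged on absolute limits (the SAP does not print the limits).
- The shift tables also use baseline. If the screening value was worse than the patient's state at first dose, later worsening can be hidden.

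These tables support the first secondary objective, safety and tolerability, so a pre-dose abnormality should not be reported as one arising on asciminib.

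**Working it through.** The plan states no figure to reproduce. The check is a reading of the date rules, followed by an illustration of size.

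**1. Which values are misplaced**

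| Value dated on the first-dose date | Can be baseline? | Period assigned | Correct? |
|---|---|---|---|
| Taken before the first tablet | No | On-treatment | No |
| Taken after the first tablet | No | On-treatment | Yes |

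The safety-baseline sentence is loosely punctuated, and the date limit could be read as applying to unscheduled assessments only. The ECG sentence supports the strict reading. The three periods are introduced for adverse-event reporting, but SAP 2.1.1 then applies the on-treatment period to safety summaries generally. I found no pre-dose exception for laboratory values or vital signs.

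**2. Is Day 1 collection pre-dose?** The documents do not settle it.

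- *Pointing to post-dose:* the preferred order of ECG, vital signs, then blood, combined with an ECG 2 to 3 hours after the dose.
- *Pointing to pre-dose:* that order is only preferred, and Table 8-5 includes fasting glucose. Inclusion criterion 8 and Protocol 8.1 also require low electrolytes to be corrected to normal before the first dose. A confirming sample could be drawn that same day.
- *Not usable:* a footnote to Table 8-1 mentions samples before the first dose and 2 to 4 hours after it, but in the available text it cannot be tied to the safety laboratory rows.

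The Week 1 Day 1 visit has a window of ±1 day. The same pre-dose sample therefore counts as baseline if the first tablet is taken the next day, and as on-treatment if it is taken that day.

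**3. An example of masking.** Potassium is low at screening, corrected, and normal on a pre-dose Day 1 sample. The SAP keeps the low screening value as baseline unless a re-test was dated before Day 1. A later fall of the same grade then shows as no shift, although the patient started asciminib with a normal value.

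**4. Illustrative size.** The assumptions below are mine, not the documents': every Day 1 draw is pre-dose, visits are independent, the per-visit abnormality rate p is unrelated to drug, N = 156, and all visits are attended. Scheduled laboratory visits after Day 1 number k = 7 to Week 48 (Weeks 2, 4, 8, 12, 24, 36, 48). To Week 144 there are k = 15 (adding Weeks 60, 72, 84, 96, 108, 120, 132 and 144), without the extra visit after dose escalation.

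Share with at least one abnormal value, Day 1 counted: 1 − (1 − p)^(k+1). Not counted: 1 − (1 − p)^k. Excess: p(1 − p)^k.

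For p = 5% and k = 7: 1 − 0.95^8 = 33.7%; 1 − 0.95^7 = 30.2%; excess 3.49 points; 156 × 0.0349 = 5.4 patients.

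| p | Week 48: with / without Day 1 | Excess (points; patients) | Week 144: with / without Day 1 | Excess (points; patients) |
|---|---|---|---|---|
| 1% | 7.7% / 6.8% | 0.93; 1.5 | 14.9% / 14.0% | 0.86; 1.3 |
| 2% | 14.9% / 13.2% | 1.74; 2.7 | 27.6% / 26.1% | 1.48; 2.3 |
| 5% | 33.7% / 30.2% | 3.49; 5.4 | 56.0% / 53.7% | 2.32; 3.6 |
| 10% | 57.0% / 52.2% | 4.78; 7.5 | 81.5% / 79.4% | 2.06; 3.2 |

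If only a fraction f of Day 1 draws is pre-dose, multiply the excess by f. At f = 0 it is zero.

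**The case against.** The strongest reply is that nothing shows Day 1 values to be pre-dose, and the only ordering guidance suggests that they follow the post-dose ECG. For post-dose values the SAP is right. This stands, and it limits the point to values that were in fact pre-dose.

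It can also be said that the date cut is a coherent convention: the protocol labels the Day −28 to −1 visit as screening/baseline and starts the on-treatment period on the day of first dose. Laboratory data are also summarized by visit and fully listed, so Day 1 values can be found. This stands too, but it does not correct the worst-value and shift tables, which do not separate Day 1 out.

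A reader might infer more than the documents support:

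- **That every treated patient is affected.** This would need all Day 1 draws to be pre-dose and on the dosing date. Neither is stated.
- **That carry-over from the previous TKI distorts baseline throughout the trial.** The protocol's mention of intolerance to ongoing TKI treatment concerns the additional cohort of up to 30 patients in MMR. If a prior TKI continued close to Day 1, a Day 1 baseline would carry its effect as well.
- **That a poor screening baseline hides later rises in all laboratory tables.** Worst post-baseline grade is tabulated regardless of baseline, and the liver categories are multiples of the ULN. Among the laboratory outputs, masking is confined to the shift tables.
- **That untimed Day 1 values should be assumed pre-dose.** If sites followed the preferred order, this would move drug-exposed values into baseline.

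**Conclusion.** The point holds in limited form. The SAP has no rule for same-day pre-dose safety values, and the rule it has gives the wrong answer for each of them. Where this occurs, worst-grade and liver-category counts can only stay the same or get worse, as can notable-value counts on absolute limits. Shift tables may in addition hide worsening.

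The number of patients affected cannot be derived from the documents. The illustration gives about 0.9 to 4.8 percentage points to Week 48 and 0.9 to 2.3 to Week 144. It rests on assumed abnormality rates, independent visits and all draws being pre-dose, so at those rates it is an upper case with respect to collection time. The true excess may be zero.

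The tables are descriptive. The primary MMR test uses the separate efficacy baseline and is unaffected. The change is worth making because it is cheap and correct whichever way sites collected the samples.

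**What to change.** **SAP 2.1.1**

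1. Define safety baseline as the last assessment before the first dose, by date and time where times are recorded.
2. Exclude first-dose-date values shown to be pre-dose from post-baseline and worst-on-treatment derivations.
3. Keep post-dose values, including the ECG at 2 to 3 hours, as on-treatment.
4. Where the time relative to dose is not recorded, keep the present date rule (on-treatment) and report the number of such values.

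**Protocol Table 8-1:** state the Week 1 Day 1 collection timing for laboratory samples, vital signs and weight. This helps only patients not yet dosed; Amendment 01 records 91 already treated by 10 August 2022. The SAP change is therefore the essential part.

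**Cost:** minor programming and no new samples. The documents do not show that clock times are collected for laboratory draws or for the first dose, so some pre-dose values may lack a time and stay classed as on-treatment. The reported count would show how far that limits the correction.

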6.6.2 Dose escalation

For patients not in MMR at 48 weeks or losing the response after the week 48 assessments up to week 108, a dose escalation to 200 mg q.d. may be considered for patients on 40 mg b.i.d. or 80 mg q.d., if in the investigator's opinion the patient may benefit from the escalation. In addition, there must not be any grade 3 or 4 toxicity while on therapy, or persistent grade 2 toxicity, possibly related to asciminib and unresponsive to optimal management.

Patients with dose reduction to 40 mg due to side effects may receive a dose escalation to 200 mg daily if the event requiring the dose reduction has disappeared and the patient has been treated at least 3 months on the standard dose of 80 mg.

CCI [REDACTED] will be performed in patients not reaching MMR at 48 weeks or patients losing the response after the week 48 assessments up to week 108, and for whom a dose escalation might benefit the patient, to identify potential BCR-ABL mutations that could confer resistance to asciminib. With the limited information on mutations no general treatment recommendations can be given for individual mutations.

Dose escalation may be performed at week 60 for patients not in MMR at week 48. For patients losing the response after week 48 up to week 108, dose escalation may be performed up to week 120 after confirmed loss of MMR in 2 consecutive tests and CCI [REDACTED] results are available.

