2.5.6 Supplementary analyses

The FAS will be used for subgroup analyses.

Subgroup analyses of the primary efficacy endpoint to assess the homogeneity of the treatment effect across demographic and baseline disease characteristics may be conducted on the following subgroups, if there are enough subjects in each category:

- Gender: Male and Female
- Race: Asian, Caucasian, or others

- Age at baseline (≥ 18 -< 65 years, ≥ 65 years, ≥ 75 years)
- Reason for discontinuation of the last prior TKI: Warning or failure (i.e. lack of efficacy) or intolerance (i.e. adverse event, lack of tolerability) to the most recent TKI therapy at the time of screening

Note: Only one reason for discontinuation is allowed for each prior therapy.

- Number of prior TKI therapies: 2, 3 or ≥ 4
- Cytogenetic response status at baseline: Major (MCyR) - 0 to 35% Ph+ metaphases; Complete (CCyR) - 0% Ph+ metaphases; Partial (PCyR) - >0 to 35% Ph+ metaphases; Minor (mCyR) - >35 to 65% Ph+ metaphases; Minimal - >65 to 95% Ph+ metaphases; or None - >95 to 100% Ph+ metaphases.
- Prior TKI treatment: imatinib, nilotinib, dasatinib, bosutinib, radotinib or ponatinib
- Prior ponatinib: Yes or No
- Mutation status at baseline: Non-mutant or mutant

For the subjects with dose escalation to 200 mg q.d. after week 48, the MMR rate and its 95% confidence interval based on the Clopper-Pearson method at week 96 and week 144 will be presented based on FAS.

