2.6.1.3 Other secondary efficacy endpoints

Time to treatment failure (TTF) is defined as the time from date of randomization to an event of treatment failure define as BCR::ABL1 > 1% IS. The following events will constitute ‘treatment failure’ for analysis purpose, and are based on the ELN criteria 2020 defining failure of a second line treatment adapted to include discontinuation of randomized treatment as an event:

- BCR::ABL1 >1% IS at 48 weeks after initiation of therapy or no complete cytogenetic response at 48 weeks.
- Subject demonstrates new T315I mutation
- Subject shows lack or loss of response such as “Loss of CHR, CCyR or PCyR at any time after initiation of therapy OR confirmed loss of MMR”
- Progression to AP/BC

For subjects who have not reached treatment failure, their TTFs will be censored at the time of last study assessment (PCR, cytogenetic, hematologic or extramedullary) before the cut-off date.

TTF (in months) is calculated as: (date of treatment failure or censoring date (see [Section 2.6.2](#)) - date of randomization + 1)/30.4375.

Progression-Free-Survival (PFS) is defined as the time from the date of randomization to the earliest occurrence of documented disease progression to AP/BC or the date of death from any cause before the cut-off date. The time will be censored at the date of last study assessment (PCR, cytogenetic, hematologic or extramedullary) or last post-treatment follow-up for subjects without event.

PFS (in months) is calculated as: (date of disease progression/death or censoring date (see [Section 2.6.2](#)) - date of randomization + 1)/30.4375.

Overall survival (OS) is defined as the time from the date of randomization to the date of death. Subjects who are alive at the time of the analysis data cutoff date will be censored at the date of last contact (see [Section 2.1.1](#)) before the cut-off date. OS (in months) is calculated as: (date of death or censoring date (see [Section 2.6.2](#)) - date of randomization + 1)/30.4375.

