5.4.4 Treatment Failure

In the event of treatment failure the subject should be discontinued from the study treatment. The ELN criteria 2020 do not make provisions for treatment failure in 3rd line however they define that a level of BCR::ABL1 $> 1\%$ IS and failure to achieve CCyR is not sufficient for optimal survival. The following events will constitute ‘treatment failure’:

- BCR::ABL1 $> 1\%$ IS at 48 weeks after initiation of therapy or no complete cytogenetic response at 48 weeks.
- Subject demonstrates new T315I mutation.
- Subject shows lack or loss of response such as “Loss of CHR, CCyR or PCyR at any time after initiation of therapy OR confirmed loss of MMR”.
- Progression to AP/BC.
- Subjects fulfilling treatment failure criteria above but without alternative treatment options may however be continued on study drug if in the investigators opinion they are obtaining benefit from the drug. Subjects with BCR::ABL 1 greater than 10%

after 48 weeks of treatment or subjects with signs of progression to AP and BC must however be discontinued.

- Subjects with newly emerging T315I mutation and lack or loss of response. While asciminib has known activity against CML with additional T315I mutation, the recommended dose of 200 mg bid for the treatment of T315I is not in use in the study. In case a subject demonstrates a new T315I mutation on asciminib, subjects should not continue in the study.

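### The MMR analysis of patients escalated to 200 mg discards post-escalation PCR data from those who had already met an SAP failure criterion, and reads the rest at study weeks rather than time on 200 mg

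*SAP*

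**What the plan says.** SAP 2.1.1 (observation periods) closes FAS and FAS 2 efficacy summaries, apart from OS and PFS, at the EoT visit or at treatment failure, whichever comes first. It adds: "The efficacy assessments collected post-treatment failure or post-EoT visit are not included in any efficacy analyses (except for OS and PFS analyses"). The excluded assessments are only listed and flagged.

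SAP 5.4.4 defines treatment failure. Its criteria include BCR::ABL1 above 1% "IS at 48 weeks after initiation of therapy or no complete cytogenetic response at 48 weeks", and a lack or loss of response, described as loss of CHR, "CCyR or PCyR at any time after initiation of therapy OR confirmed loss of MMR". SAP 2.6.1.3 repeats these criteria for TTF, where they are said to serve "for analysis purpose, and are based on the ELN criteria 2020 defining failure of a second line treatment". Under SAP 5.4.4, patients who meet them but are "without alternative treatment options may however be continued on study drug" if the investigator sees benefit.

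Protocol 6.6.2 opens 200 mg q.d. to two groups. Patients not in MMR at Week 48 may escalate at Week 60. For later loss of response, "dose escalation may be performed up to week 120 after confirmed loss of MMR in 2 consecutive tests".

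SAP 2.5.6 contains the only visible planned MMR analysis of these patients: "For the subjects with dose escalation to 200 mg q.d. after week 48, the MMR rate and its 95% confidence interval" by the Clopper-Pearson "method at week 96 and week 144 will be presented based on FAS". It does not lift the SAP 2.1.1 rule and does not say how patients with excluded data are counted.

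**The concern.** The event that qualifies a patient for escalation can also be the event that ends that patient's efficacy data. A patient who loses MMR, escalates and regains MMR on 200 mg could then appear in the escalation analysis with no usable result.

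Protocol 1.2 gives the possible benefit of escalation as one of the trial's purposes, and Protocol 12.3 leaves the escalation analyses to the SAP. A rate that is biased or selective through its own data rule would not answer that question.

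The second problem is separate. SAP 2.1.1 starts the molecular-response clock at randomisation, whereas escalation can happen at any 12-weekly visit from Week 60 to Week 120 (Protocol Table 6-2 footnote). One study week therefore corresponds to very different exposures to 200 mg, and at Week 96 to none at all for some patients.

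**Working it through.** **1. The plan's own figure.** The only design calculation concerns the primary test: N = 156, null 0.23, alternative 0.33, one-sided 0.025 (Protocol 12.8.1, SAP 3). The exact binomial test rejects from 47 responders, with attained alpha 0.0241 and power 0.801, so the stated 80% reproduces. Escalation starts at Week 60, so this test is essentially untouched. No sample size or precision is given for the escalation analysis.

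**2. Escalation routes set against the SAP failure criteria.**

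| Route to 200 mg | SAP failure criterion already met? | Post-escalation PCR usable in SAP 2.5.6? |
|---|---|---|
| Confirmed loss of MMR after Week 48 | Yes, where the loss also meets the SAP 5.4.1 confirmation rule | No |
| Not in MMR at Week 48, with BCR::ABL1 >1% or no CCyR, and kept on drug | Yes | No |
| Not in MMR at Week 48, BCR::ABL1 >0.1–1%, in CCyR | Not by the Week-48 criteria | Yes |

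Two details affect the size of the second row. SAP 5.4.2 treats missing cytogenetics as no CCyR unless the patient is in MMR, which may add patients. BCR::ABL1 above 10% after 48 weeks requires discontinuation, which removes some.

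**3. How the excluded patients would be counted.** SAP 2.6.2 makes a patient with no available assessment at a time point a non-responder. SAP 5.5.1 places those continuing after treatment failure in a subdivision of its missing category. Together these point to non-response, although SAP 2.5.6 does not say so.

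**4. Size at Week 144.** Let f be the share of escalators who failed before escalating, and p_nonfail and p_fail the true MMR rates in the two groups. If failed patients count as non-responders:

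- reported = (1 − f) × p_nonfail
- true = (1 − f) × p_nonfail + f × p_fail
- loss = f × p_fail

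None of the three inputs is in the documents. With p_nonfail assumed at 30%:

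| f | Reported | Loss, p_fail = 30% | Loss, p_fail = 15% | Loss, p_fail = 5% |
|---|---|---|---|---|
| 0% | 30% | 0 | 0 | 0 |
| 25% | 22.5% | 7.5 | 3.75 | 1.25 |
| 50% | 15% | 15 | 7.5 | 2.5 |
| 75% | 7.5% | 22.5 | 11.25 | 3.75 |
| 100% | 0% | 30 | 15 | 5 |

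Losses are in percentage points. As an example, assume 40 escalators with 12 truly in MMR, and half of all escalators and of the responders already failed. The report would be 6/40 = 15.0% (95% CI 5.7–29.8%) instead of 12/40 = 30.0% (16.6–46.5%).

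If failed patients are dropped instead, the rate is p_nonfail and describes only non-failing escalators. At f = 50%, p_nonfail = 30% and p_fail = 15%, it would read 30% against a true 0.5 × 30 + 0.5 × 15 = 22.5%.

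**5. Time on 200 mg at the two readings** (analysis week minus escalation week):

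| Escalation visit (week) | 60 | 72 | 84 | 96 | 108 | 120 |
|---|---|---|---|---|---|---|
| At Week 96 | 36 | 24 | 12 | 0 | −12 | −24 |
| At Week 144 | 84 | 72 | 60 | 48 | 36 | 24 |

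The longest possible time on 200 mg is 144 − 60 = 84 weeks, so Weeks 96 and 144 cannot mean weeks since escalation. By SAP Table 2-1 the Week-96 window runs from day 96 × 7 − 40 = 632 to day 96 × 7 + 43 = 715, and the Week-108 target is day 108 × 7 + 1 = 757. Patients escalating at Week 108 or 120 are therefore read at Week 96 before any 200 mg. One who loses MMR only after Week 96 can count there as a responder on pre-escalation data, so the Week-96 bias can go either way.

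**The case against.** The analysis is one descriptive sentence among the supplementary analyses, with no test and no stated estimand. The separate category in SAP 5.5.1, and a primary endpoint that already requires no prior failure, suggest that the cut at failure is deliberate. This limits the weight of the point. It does not make a cut at failure suitable for an analysis of what happens after escalation.

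The point depends on which failure definition applies. Protocol 9.1.1 lists only the Week-48 criteria as treatment failure, and the TTF list in Protocol 12.5.1 does not mention loss of MMR. Under the protocol definitions, patients escalating solely for loss of MMR would keep their data. That dependence is real, but SAP 5.4.4 is the natural definition for a rule in the SAP.

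The affected share may be small. SAP 5.4.1 asks for a confirming sample within 4 to 6 weeks, scheduled PCR is 12-weekly, and the escalation rule asks for two consecutive tests, so the two are not stated to be identical. Protocol 8.3.1.1 does, however, define confirmed loss in the same terms as the SAP, and Protocol 8.4.2 allows unscheduled samples to confirm loss of response. Patients failing at Week 48 should generally stop treatment. f is therefore unknown, and the table shows a range rather than a forecast.

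Weeks 96 and 144 fit the planned analyses, and at Week 144 every escalator still on treatment has had at least 24 weeks since the first 200 mg dose. The data cut-off rule in SAP 2.1 also limits how many late escalators enter the 96-week analysis. It does not remove the mixing when the Week-96 rate is reported at the end-of-treatment analysis.

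**Conclusion.** The concern holds. SAP 2.1.1 and SAP 2.5.6 conflict for escalators who met an SAP failure criterion before escalating. Counted as non-responders, they lower the Week-144 rate by f × p_fail; dropped, they leave a rate for a selected subgroup. The size cannot be fixed from the documents because f and both response rates are assumptions. The finding also rests on SAP 5.4.4 being the definition behind the cut. Escalators at >0.1–1% with CCyR at Week 48 are not affected by the Week-48 criteria.

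The Week-96 figure mixes readings before and after 200 mg whichever failure definition is used. The escalation safety and ECG summaries are not affected. This should be fixed, but it does not threaten the primary result.

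**What to change.** 1. Add one exception to SAP 2.1.1: for the SAP 2.5.6 escalation analysis, keep on-treatment assessments from the first 200 mg dose to the EoT visit, regardless of earlier treatment failure. State also how the analysis treats a failure criterion met after that dose, and data collected after a return to 80 mg.
2. In SAP 2.5.6, report MMR at fixed times after the first 200 mg dose, for example 12 and 24 weeks, using the escalation reference date already in SAP 2.1.1. Write in the counting rule: all escalators in the denominator, missing as non-response. For the 96-week analysis, say how readings not yet due at the cut-off are handled.
3. For the FAS-wide MMR, MR4 and MR4.5 rates after Week 48, keeping or lifting the cut is an estimand choice. A sensitivity analysis that retains on-treatment post-failure data would be enough.

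The cost is SAP wording and programming. The PCR schedule in Protocol Table 8-2 already supplies both readings for every escalation visit: Weeks 72 and 84 after Week 60, and so on to Week 132 and EOT at Week 144 after Week 120. No dose, visit or management rule changes.
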